2.2 Aims and Objectives of the Study

Our rationale for examining a genotype-guided approach to acute and chronic pain management is based on the importance of *CYP2D6* for the bioactivation of tramadol, codeine, and hydrocodone and data from a pilot study supporting improved pain control in IM/PMs in the genotype-guided arm who are taking these drugs at baseline. Similarly, the rationale for examining a genotype-guided approach to depression medication therapy is based on the demonstrated role of *CYP2D6* in the bio inactivation and *CYP2C19* oxidation of select, commonly used SSRIs. Secondly, data from industry sponsored trials support the hypothesis of improved symptom control in a genotype-guided arm.

Acute Pain: Determine if a genotype-guided approach to acute post-surgical pain therapy leads to improved pain control compared to usual care, as defined by a decrease in the SIA score. Secondarily, we will evaluate whether this approach leads to reduced use of DEA Schedule II opioids and reduced pain intensity.

Chronic Pain: Determine if a genotype-guided approach to pain therapy in participants with at least 3 months of chronic pain leads to improved pain control compared to usual care.

Depression: Determine if genotype-guided dosing or selection of antidepressants among participants with at least 3 months of depressive symptoms who require new or revised antidepressant therapy leads to improved control of depression, compared to usual care.

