CYP2D6 phenotypes will be inferred based on the activity scoring system as shown in **Table 2 and Table 3**. The activity score value of each allele (**Table 2**) is added together to determine the total activity score for the diplotype. The activity scores are converted to phenotypes per **Table 3**. The IM phenotype will be defined as an activity score of >0 to 0.75, not >0.75 to 1.0. As there is debate about

how to define the IM phenotype, we will have an *a priori* analysis plan to determine whether participants in the usual care arm with an activity score of >0.75 to 1 (who we will define as NM) have worse pain control or depressive symptoms than NMs with an activity score > 1 to 2. If an allele is duplicated, and it is unknown which allele is duplicated, then the AS may be a ranged number, resulting in a ranged phenotype. If the ranged phenotype is NM-UM, the individual will be treated clinically as is if they were a UM.

Table 2. CYP2D6 allele to activity score

Alleles	Activity value+
*1, *2	1
*9, *14, *17, *29, *41	0.5
*10	0.25
*3, *4, *5, *6, *7, *8	0

+ Lab reported results may use older versions of CPIC guidelines for activity value definitions

Table 3. CYP2D6 phenotype by Activity Score

Inferred CYP2D6 phenotype	CYP2D6 activity score (AS)
UM	> 2.0
NM	>0.75 to 2.0
IM*	>0 to 0.75
PM	0

*This phenotype definition differences from current CPIC guidelines and may be different from what appears in the lab reported phenotypes

CYP2C19 phenotypes will be inferred from the genotypes, as shown in **Table 4**.

Table 4. CYP2C19 phenotype by genotype

Inferred CYP2C19 phenotype	Example CYP2C19 genotypes
UM	*17/*17
RM	*1/*17
NM	*1/*1
IM	*1/*2, *1/*3, *2/*17, *3/*17
PM	*2/*2, *2/*3, *3/*3

The CYP2C19 metabolizer phenotype and the CYP2D6 metabolizer phenotypes and/or activity scores will be included in the PGx testing report generated by the laboratory, which is then returned to the provider and deposited in the EMR, where available.

Clinical Decisions Support / Clinical Recommendations

Acute and Chronic Pain

Standardized clinical consult notes with or without pharmacogenetics expert consultations will be generated based on the genotype-inferred phenotype, and in the case of drugs including *CYP2D6* guidance, will include consideration of drug interactions.

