Medication side effects. The frequency and severity of medication side effects within each trial and trial arm will be summarized using standard descriptive statistics for discrete data (counts and percentages).

Acute Pain

Trends in endpoints. In addition to the primary and secondary endpoints described above, we will compare the time trends in the endpoints: pain scores, opioid usage, opioid misuse score, and mobility score at baseline, 1, 3, and 6 months among the CYP2D6 IM or PM subgroup, using a repeated-measures mixed effect model or generalized repeated-measures mixed effect model, as appropriate. Since participants are randomized to Intervention and Control groups and not to the CYP2D6 IM or PM subgroup within Intervention and Control groups, there could be important differences in baseline characteristics between the two groups. For these reasons, we will conduct covariate-adjusted repeated measures mixed models that will account for differences in baseline characteristics that differ between the Intervention – CYP2D6 IM or PM subgroup and the Control – CYP2D6 IM or PM subgroup. Potential baseline characteristics may include age, sex, income, education, insurance, surgical procedure type. We will select the appropriate covariance matrix (e.g. compound symmetry, autoregressive, unstructured, or other covariance structure) based on the data.

Difference within the NM group. In the control arm participants, we will compare pain scores in participants with a CYP2D6 activity score $>0.75 - 1$ to participants with an activity scores $>1-2$ using a two-sided two-sample t-test or Mann Whitney test, as appropriate, with a type 1 error of 0.05. Additionally, we will use linear regression to adjust for differences in baseline characteristics.

Chronic Pain

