Trends in endpoints. In addition to the primary and secondary endpoints described above, we will compare the time trends in the endpoints: pain control, pain reduction, clinically significant pain reduction, and opioid misuse score at baseline, 1, 3, and 6 months among the CYP2D6 IM or PM subgroup, using a repeated-measures mixed effect model or generalized repeated-measures mixed effect model, as appropriate. Since participants are randomized to Intervention and Control groups and not to the CYP2D6 IM or PM subgroup within Intervention and Control groups, there could be important differences in baseline characteristics between the two groups. For these reasons, we will conduct covariate-adjusted repeated measures mixed models that will account for differences in baseline characteristics that differ between the Intervention – CYP2D6 IM or PM subgroup and the Control – CYP2D6 IM or PM subgroup. Potential baseline characteristics may include age, sex, income, education, insurance, and medical conditions. We will select the appropriate covariance matrix (e.g. compound symmetry, autoregressive, unstructured, or other covariance structure) based on the data.

Difference within the NM group. In the control arm participants, we will compare pain scores and pain control in participants with a CYP2D6 activity score $>0.75 - 1$ to participants with an activity scores $>1-2$ using a two-sided two-sample t-test or Mann Whitney test, as appropriate, with a type 1 error of 0.05. Additionally, we will use linear regression to adjust for differences in baseline characteristics.

Depression

Trends in endpoints. In addition to the primary and secondary endpoints described above, we will compare the time trends in the endpoint depression symptom scores at baseline, 1, 3, and 6 months among the CYP2D6 PM or UM or CYP2C19 UM, RM or PM subgroup, using a repeated-measures mixed effect model. Since participants are randomized to Intervention and Control groups and not to the CYP2D6 PM or UM or CYP2C19 UM, RM or PM subgroup within Intervention and Control groups, there could be important differences in baseline characteristics between the two groups. For these

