14. APPENDICES

14.1 APPENDIX A. SIA SCORE BACKGROUND AND RATIONALE

For the primary endpoint, we propose to use a composite score that captures both opioid consumption (MED) and pain intensity. This is based on preliminary data from a University of Florida (UF) pilot study in which CYP2D6 genotype-guided opioid prescribing after arthroplasty surgery was compared to a usual care approach (ClinicalTrials.gov Identifier: NCT03534063). While not powered to detect differences in clinical endpoints, preliminary results from 174 patients showed similar pain intensity at 2-week post-surgery between genotype-guided and usual care groups, but significantly lower MMEs in the genotype-guided group. The combination of lower opioid consumption with similar pain intensity indicates better pain control in the genotype-guided arm. However, assessing opioid consumption and pain intensity as two separate variables fails to characterize the inter-individual differences in opioid use as pain intensity changes over time, which is why we believe a composite endpoint that integrates the two is justifiable.

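### The acute-pain check of the CYP2D6 activity-score cut-off uses pain scores only; adding opioid usage and SIA would let it see a deficit that appears mainly as extra opioid use

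*Combined protocol and SAP*

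**What the plan says.** Section 7.1 defines IM as an activity score >0 to 0.75, acknowledges that the boundary is debated, and notes under Table 3 that it differs from current CPIC guidelines. It commits to an a priori analysis of whether usual-care participants with scores >0.75-1 "have worse pain control or depressive symptoms than NMs with an activity score" above 1 and up to 2.

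Section 10.6 (Acute Pain, Difference within the NM group) carries this out: "In the control arm participants, we will compare pain scores in participants with a CYP2D6 activity score" of >0.75-1 against >1-2, "using a two-sided two-sample t-test or Mann Whitney test, as appropriate, with a type 1 error of 0.05", plus a linear regression adjusting for baseline differences. Pain scores are the only outcome named.

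Three other places bear on that choice:

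- Section 2.2 asks whether the genotype-guided approach to acute pain "leads to improved pain control compared to usual care, as defined by a decrease in the SIA score".
- Appendix A justifies SIA from the pilot, where "preliminary results from 174 patients showed similar pain intensity at 2-week post-surgery between genotype-guided and usual care groups, but significantly lower MMEs" were seen in the guided group. It argues that "assessing opioid consumption and pain intensity as two separate variables fails to characterize the inter-individual differences in opioid use" as pain changes over time.
- The parallel chronic-pain check in 10.6 names two outcomes: "we will compare pain scores and pain control in participants with a CYP2D6 activity score" in the two bands. The depression check likewise names depression scores and depression control.

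**The concern.** Post-surgical patients can adjust how much opioid they take. Someone who gets less relief per dose may take more and report the same pain. Appendix A relies on this reasoning when it rejects pain or opioid use alone as the primary endpoint. The acute-pain check looks at one of the two SIA components and leaves out the other.

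This is the one specified analysis that addresses whether participants just above the 0.75 boundary do worse under usual care. If they did worse mainly through higher opioid use, the check as written would tend to return a null, and that null could be misread as support for the boundary. What is at stake is the interpretation of one exploratory analysis, not the primary comparison.

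**Working it through.** **Can pain scores be read to include opioid use?** No. The acute-pain trend analysis in the same part of 10.6 lists "pain scores, opioid usage, opioid misuse score, and mobility score at baseline, 1, 3, and 6 months", with the two as separate endpoints. Section 11.2 treats them as the two inputs to SIA. That trend analysis covers only IM/PM participants, so it does not supply the missing NM comparison.

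**The plan's own figure.** The documents give no power for this check. The acute-pain primary calculation reproduces: effect 0.375, two-sided alpha 0.049 and 90% power give 151.2 per arm by the t-test, rounded up to 152 as in section 10.1; power at 152 is 90.1%. The pilot effect is 38.55/93.5 = 0.412, as stated.

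**Inputs from the documents**
- Control completers: 845 (Table 9).
- SIA SD: 93.5 (section 10.1).
- Each SIA component runs from -100 to 100 (section 11.2). If uniform, its SD is 200/√12 = 57.7. An SIA SD of 93.5 then implies a component correlation of 93.5²/(2 × 57.7²) - 1 = 0.31.

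**Assumptions**
- NMs are about 80% of controls (18% are IM/PM per section 10.1, and 1-2% UM per section 2.1): 845 × 0.80 = 676.
- 20-40% of NMs have scores >0.75-1 (not in the documents): groups of about 135/541, 203/473 and 270/406.
- The true SIA deficit is 0.25 SD, i.e. 0.25 × 93.5 = 23.4 points, two-thirds of the 0.375 planning effect.

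**Formula.** If a share s of the SIA deficit lies in the pain component, the standardized pain difference is s × 0.25 × 93.5/57.7. Two-sample t-test power at alpha 0.05, across the three group splits:

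| Share of deficit in pain | Pain difference (SD) | Pain-score test | SIA test |
|---|---|---|---|
| 0 | 0 | 5% | 74-89% |
| 25% | 0.10 | 18-25% | 74-89% |
| 50% | 0.20 | 56-73% | 74-89% |
| 62% | 0.25 | 74-89% | 74-89% |
| 75% | 0.30 | 88-97% | 74-89% |
| 100% | 0.40 | 99-100% | 74-89% |

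The crossover is at s = 57.7/93.5 = 62%. Below it SIA is the stronger outcome; above it pain is.

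**Smaller enrolment.** From the synopsis total of 1730, control completers are about 1730 × 0.90 × 0.93/2 = 724. SIA power becomes 67-84%; pain-only power is 5%, 16-22% and 49-66% at shares of 0, 25% and 50%.

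**Opioid usage as an outcome.** A simulation of ranked components with a shift in opioid use only, covering both sample sizes and all three splits, gave:

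| Opioid shift | Pain-score test | Opioid-usage test | SIA test |
|---|---|---|---|
| 0.3 SD | 4-5% | 81-96% | 42-63% |
| 0.5 SD | 5-6% | about 100% | 84-97% |

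When the deficit is confined to opioid use, opioid usage itself is more sensitive than SIA.

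**The case against.** The strongest counter-arguments, and what stands of each:

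- **The pilot does not show this pattern for activity score 1.** A reader might infer that it does. It compared guided with usual-care arms, not activity-score bands within usual care, so prescribing guidance could itself have lowered opioid use. Appendix A also describes the pilot's SIA result as less pain with fewer opioids in the guided arm (p=0.07), so the difference was not purely in opioid use. This stands in full: the pilot shows that such a pattern is possible, nothing more.
- **The 5% figure is a tautology.** Any test has power equal to its alpha on a variable that does not differ. This stands; the informative rows are the intermediate ones.
- **Pain alone can be the better outcome.** It stands for shares above about 62%, and is why pain should not be dropped.
- **Section 11.2 defines pain control by pain intensity.** This softens the conflict with 7.1, since a pain-only check can be squared with the data dictionary. But section 2.2 is specific to acute pain and uses SIA. The text is ambiguous rather than flatly contradictory.
- **Other analyses could cover it.** Section 10.6 lists activity scores among the subgroups to be considered and defers detail to a separate SAP. A reader might therefore go too far in saying that an opioid-use deficit cannot be detected in this trial. The list, however, names neither an opioid or SIA outcome nor the >0.75-1 versus >1-2 contrast, so it does not replace the promised a priori check.
- **Nothing hangs on the result.** No decision rule depends on it, and section 10.3 fixes the primary population at scores ≤0.75. This stands and limits the severity.

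**Conclusion.** The point holds as a low-severity improvement. The specified acute-pain check examines only one component of the outcome by which section 2.2 defines acute-pain control. It would largely miss a deficit expressed mainly as higher opioid use: 5-25% power with at most a quarter of the deficit in pain, against 74-89% for SIA. The ordering reverses once more than about 62% of the deficit is in pain. These figures rest on an assumed 0.25 SD deficit, an assumed 20-40% share with scores >0.75-1, about 80% NM, and uniform SIA components.

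The documents do not support two stronger readings: that participants with a score of 1 have such a deficit, or that the primary acute-pain analysis is compromised.

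**What to change.** In section 10.6 (Acute Pain, Difference within the NM group), keep pain scores and add two outcomes: day-10 opioid usage and the 10-day SIA score. Use all three in both the two-sample test and the covariate-adjusted regression. State the set of participants in which the SIA ranks are computed, for example NM controls only or all randomized participants, because the score depends on it. Replacing pain with SIA as a single lead outcome is not needed, since neither is more sensitive throughout.

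Cost: a line or two of wording and two more outcomes in an exploratory analysis. No new data are required; section 7.3 already collects pain intensity and opioid consumption from all acute-pain participants at 10 days.

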PROMIS pediatrics 37 – Pediatric study participants (ages 8-17) will complete a 37-question survey assessing pediatric well-being and sub domains: pain interference, physical function, sleep disturbance, social role and activities functioning, fatigue, anxiety, and depression. This survey will be administered to pediatric participants at baseline, 1-month, 3-months, and 6-months post-surgery (acute pain), or baseline, 1 month, 3 months, and 6 months post return of results (depression).

Health care utilization – Survey of the number of significant cost driver health care encounters (e.g. hospitalizations, clinic visits, etc.). This survey will be administered to participants at 10-day, 1-month, 3-months, and 6-months post-surgery (acute pain), or baseline, 1-month, 3-months, and 6-months post return of results (chronic pain, depression).

Medications - Participant medications will be collected using patient surveys at baseline and the primary endpoint time points: 10-days for Acute Pain and 3-months for Depression and Chronic pain.

Productivity loss – Survey of loss of work the time and pay lost due to the participant's depression or pain. This survey will be administered to participants at 1-month, 3-months, and 6-months post-surgery (acute pain), or 1-month, 3-months, and 6-months post return of results (chronic pain, depression).

Acute Pain:

PROMIS Numeric Rating Scale - Pain Intensity - An 11-point numeric scale ranging from 0 (no pain) to 10 (worst possible pain) for average pain. This survey will be administered to all participants at baseline, 10 days, 1-month, 3-months, and 6-months post-surgery.

PROMIS pain intensity scale – A participant completed 3-question survey of average pain over the last 7 days, worst pain over the last 7 days, and current pain. Each question is on a 1-5 integer scale, the higher the value, the more intense the pain. This survey will be administered to all participants at baseline, 10 days, 1-month, 3-months, and 6-months post-surgery.

Opioid consumption questionnaire – A participant completed survey of pain prescription medication consumption, including the type of opioid pain medication, number of pills dispensed, if a refill has been obtained, and the number of pills left for each opioid pain medication selected. This survey will be administered to all participants at 10 days and 1-month post-surgery.

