11.2 Data Element Definitions

Clinically significant pain reduction: Whether or not the pain reduction score is ≤ 0.7 . If the pain reduction score is ≤ 0.7 , clinically significant pain reduction is achieved, if pain reduction scores is > 0.7 , clinically significant pain reduction is not achieved.

Depression symptom control: The change in the PROMIS Emotional Distress - Depression 8b or PROIMIS pediatric Depression 8a survey depression score from baseline to time t.

Depression remission: A. Whether or not the summed raw PROMIS emotional distress depression 8b survey responses are ≤ 16 , which is equivalent to the participant responding “rarely” or “never” to most or all of the PROMIS emotional distress - depression 8b survey questions. B. Whether or not the PHQ-8 scores are ≤ 4 , which is equivalent to depression severity being none-mild.

Depression (PHQ-8) score: The sum of the responses to the PHQ-8 survey, range from 0 to 24.

Depression (T) score: The T-score converted summed responses to the PROMIS emotional distress depression 8b survey. The T-score conversion is centered around 50 with standard deviation of 10.

Depression severity: The depression score converted to depression severity (none, mild, moderate, severe) based on the scoring guide for the PROMIS emotional distress depression 8b survey.

Medication adherence: The scored responses to the Voils Medication Adherence survey.

Medication concordance: Whether or not the medication the participant is prescribed after the intervention is concordant with the participants CYP2D6 and, for the depression trial, CYP2C19 phenotype.

Medication side effects severity burden: (Depression only) The sum of the scored severity (none = 0, mild = 1, moderate = 2, severe = 3) for common SSRI side effects.

Opioid misuse score: The T-score converted summed responses to the PROMIS prescription medication misuse 7a survey. The T-score conversion is centered around 50 with standard deviation of 10.

Opioid persistence: Defined as ≥ 1 opioid prescription refill between 90 days and 180 days after the surgical procedure.

Opioid usage: The average daily morphine equivalents in mg (MED) in past 7 days. MEDs will be calculated using data from the opioid usage survey.

Overall well-being: Defined as the T-score converted summed responses to the PROMIS 43/PROMIS 37 pediatrics survey. The T-score conversion is centered around 50 with standard deviation of 10.

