Pain control: The difference in pain intensity score at follow-up time t and the baseline pain intensity score.

Pain intensity score: The mean of average pain in the last 7 days, current pain, and worst pain in the last 7 days. Average pain, current pain, and worst pain will be collected using the 3-question PROMIS pain intensity scale.

Pain reduction score: The ratio of the pain intensity score (derived from the PROMIS pain intensity survey) at follow-up time t to the baseline pain intensity score.

Silverman integrative analgesic assessment (SIA) score: This is an integrated measure of pain and opioid usage, calculated as follows: pain and opioid usage are ranked, the ranks are converted to percentiles and linearly transformed such that the scores are centered at 0 and range -100 to 100. The pain scores and opioid usage transformed percentiles are summed to generate the SIA score that ranges -200 to 200. Negative values indicate low pain with minimal opioid usage, while positive values indicate higher pain with higher opioid usage. See Appendix A for additional details and supporting rationale.

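### Two exploratory time-trend analyses in section 10.6 cannot be carried out as written: acute-pain opioid usage has data at one listed visit, and three chronic-pain endpoints are constant at baseline

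*Combined protocol and SAP*

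**What the plan says.** All references are to the combined protocol and SAP.

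**Acute pain.** Section 10.6 (Acute Pain, Trends in endpoints) compares time trends in "pain scores, opioid usage, opioid misuse score, and mobility score at baseline, 1, 3, and 6 months" in the CYP2D6 IM/PM subgroup, using mixed models. Section 7.3 says of the opioid consumption questionnaire: "This survey will be administered to all participants at 10 days and 1-month post-surgery". Table 8 agrees. Section 11.2 derives opioid usage from that survey.

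**Chronic pain.** Section 10.6 (Chronic Pain, Trends in endpoints) compares time trends in "pain control, pain reduction, clinically significant pain reduction, and opioid misuse score at baseline, 1, 3, and 6 months". Section 11.2 defines the first three of these:
- "Pain control: The difference in pain intensity score at follow-up time t and the baseline pain intensity score".
- The pain reduction score is the ratio of the pain intensity score "at follow-up time t to the baseline pain intensity score".
- "If the pain reduction score is ≤ 0.7 , clinically significant pain reduction is achieved"; above 0.7 it is not.

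**Both, and depression.** The models are to "account for differences in baseline characteristics that differ between" the two arm subgroups, drawing on a list of potential covariates. The covariance structure is to be chosen from the data, with compound symmetry, autoregressive and unstructured given as examples. Section 10.6 leaves further detail to a study SAP.

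**The concern.** A repeated-measures model needs an outcome that is observed, and that varies, at each visit it includes. The acute-pain list names visits at which opioid usage is never asked about. The chronic-pain list includes a visit at which three outcomes are fixed by their own definitions. A SAP that carries these lists over would contain one analysis that cannot be estimated and others that fail, or give a wrong standard error, depending on the covariance structure and contrast chosen.

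The stakes are limited but real. These models stand under the specified analyses of section 10.6. There they are also the plan's answer to its own worry that the actionable subgroups may differ at baseline; the primary tests in section 10.4 are unadjusted.

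**Working it through.** **1. Visits listed against visits collected** (section 10.6 against section 7.3 and Table 8)

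| Endpoint | Listed in 10.6 | Collected | Listed visits with data |
|---|---|---|---|
| Acute opioid usage | baseline, 1, 3, 6 mo | 10 d, 1 mo | 1 of 4 |
| Acute pain scores | baseline, 1, 3, 6 mo | baseline, 10 d, 1, 3, 6 mo | 4 of 4; day 10 unused |
| Acute mobility | baseline, 1, 3, 6 mo | baseline, 10 d, 1, 3, 6 mo | 4 of 4; day 10 unused |
| Misuse (both pain trials) | baseline, 1, 3, 6 mo | baseline, 3, 6 mo | 3 of 4 |

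One time point gives no trend. The only other time at which opioid usage is collected is day 10, which the list leaves out.

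**2. Chronic-pain endpoints at baseline** (section 11.2, with t set to baseline and Y₀ the baseline score)
- Pain control: Y₀ − Y₀ = 0 for everyone.
- Pain reduction: Y₀ / Y₀ = 1 for everyone.
- Clinically significant reduction: the ratio 1 exceeds 0.7, so not achieved for everyone.

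**3. Consequences for the fitted model.** The plan gives no figure for these models. The sample they would run on is 134 per arm (section 10.1), which reproduces: effect size 0.40, two-sided alpha 0.049 and 90% power give 134 per arm with the noncentral t.

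Assume that raw scores at the four visits have equal variance and common correlation. Let v be the variance of a change score at a follow-up visit. The covariance between two follow-up changes is then v/2, and every term involving baseline is 0.

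*Unstructured covariance.* The baseline row and column are all zero, so the 4 × 4 matrix has rank 3 and determinant 0. It cannot be fitted.

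*Compound symmetry.* The model uses one variance and one covariance, averaged over the four visits:
- Variance: (0 + v + v + v)/4 = 0.75v.
- Covariance: of 12 off-diagonal entries, 6 are 0 and 6 are v/2, so the mean is 0.25v.

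| Arm difference in | Model variance ÷ true variance | SE ratio | True size of a nominal 5% test |
|---|---|---|---|
| 3-month value | 0.75v ÷ v = 0.75 | 0.866 | 2[1 − Φ(1.96 × 0.866)] = 9.0% |
| Mean of 1, 3, 6 months | (0.75v/3 + 2 × 0.25v/3) ÷ (v/3 + 2 × 0.5v/3) = 0.625 | 0.791 | 2[1 − Φ(1.96 × 0.791)] = 12.1% |
| 3 months minus baseline | 2(0.75v − 0.25v) ÷ v = 1 | 1.000 | 5% |
| 6 months minus 1 month | 2(0.75v − 0.25v) ÷ (2v − v) = 1 | 1.000 | 5% |

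The correlation cancels. Simulation of the 3-month difference at 134 per arm gave 8.7% (4,000 trials, correlation 0.6). A shorter run of 1,000 trials at correlation 0.5 gave 6.9%, against 4.2% on the same draws with the baseline row dropped. The algebra is the figure to rely on.

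*Arm-by-time test.* Subtracting each person's baseline from every row leaves within-person contrasts unchanged. With the baseline row kept, the arm-by-time F for pain control therefore equals the F for the raw score. In 4,000 simulated trials it rejected 5.7% and 4.9% at correlations 0.3 and 0.6; the ratio endpoint rejected 5.5% and 5.2%.

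*Responder model.* In simulated data (134 per arm, visit as a category) there were no responders at baseline in either arm. A logistic fit put the baseline intercept at about −26, with arm-by-time standard errors of about 26,000. Contrasts with baseline have no finite estimate.

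**4. Covariates chosen by observed imbalance.** Simulation with one covariate, covariate–outcome correlation 0.3 to 0.7 and selection at p < 0.05 or p < 0.20 gave a type I error of 2.6% to 4.6% against a nominal 5%. The rule is slightly conservative.

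**The case against.** **The plan compares time trends, and that test is sound.** This stands for pain control and, in the simulations, for pain reduction under compound symmetry. A reader might infer that the chronic-pain trend tests as a whole run at about 9%. The documents do not support that: the 9% belongs to a visit-specific arm difference under one of several permitted structures, whereas section 10.6 names a comparison of trends. The contrasts are exactly right when raw scores are exchangeable. Under decaying correlation compound symmetry would misstate some of them, but equally so for raw scores, so the baseline row is not the cause.

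**Section 11.2 defines these quantities at a follow-up time, so baseline may be meant only as the reference.** That is a fair reading of 11.2, but section 10.6 lists baseline as a modelled time for these endpoints. A SAP sentence would settle it.

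**The analyst would see the problem and adapt.** Section 10.2 promises a check of model assumptions and section 10.6 leaves the covariance open, so a zero-variance visit would probably be noticed. Neither supplies opioid usage at visits where it is not asked. The multiple-imputation sensitivity analysis of section 10.8 cannot do so either, because nobody has an observed value at those visits.

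**The other visit gaps are small.** This largely stands. Misuse still has three usable visits. Day 10 is tested elsewhere for the SIA score, pain and opioid usage, so for pain and mobility its omission from the trends may be a choice. For opioid usage it removes the only second time point.

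**Covariate selection inflates error.** A reader might infer this, but the direction is the reverse. The argument for fixing covariates in advance is prespecification, not error control.

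**Conclusion.** The point holds, at minor severity. The acute-pain opioid-usage trend cannot be estimated from the listed visits; this follows from the documents alone. The three chronic-pain endpoints defined relative to baseline should not have a baseline row. With one, an unstructured covariance and a responder model with a categorical baseline visit both fail. Under compound symmetry the standard error of a visit-specific arm difference is about 13% too small (5% becomes about 9%), and that of the average follow-up difference about 21% too small (about 12%). These two sizes assume exchangeable raw scores with arm-by-visit means; they do not depend on the correlation.

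The constant-baseline problem does not extend to the depression model, to acute pain and mobility scores, or to the misuse score, all of which have a valid baseline. Nor do the documents support reading this as a threat to the trials' conclusions. Section 10.8 treats the repeated-measures analyses as exploratory, and the primary and secondary tests and sample sizes do not use these models.

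**What to change.** In section 10.6, or in each trial's SAP:

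- **List for each endpoint only the visits in Table 8.** Acute opioid usage at 10 days and 1 month, described as a two-visit comparison; acute pain scores and mobility at baseline, 10 days, 1, 3 and 6 months; misuse at baseline, 3 and 6 months in both pain trials.
- **Chronic pain: choose one of two routes.** Either model the raw pain intensity score at the collected visits, with baseline as an outcome or as a covariate (both are valid), or model the change, ratio and responder endpoints at 1, 3 and 6 months only. The responder endpoint should have no baseline row in any case.
- **Optional: name the covariates in advance.** The baseline score and the randomisation strata of section 4.1 are natural choices.

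The cost is a few lines of text. No new data, visits or participants are needed.
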